3.2. Changes to the Analyses from the Protocol

One exploratory efficacy endpoint was added in addition to the endpoints defined in the protocol.

- Summaries of weekly responders (defined in section 7.3) will be summarized as an exploratory efficacy endpoint.

The wording of how randomization file is handled is clarified in the SAP by saying the file will be held by an independent unblinded Biostatistician, not the study statistician.

3.3. Randomization and Blinding

This is a randomized, double-blinded, Placebo-controlled study. Patients should be randomized as close as possible to the time of the planned first dose of study drug.

Randomization will be conducted via an interactive web response system (IWRS) in a 1:1:1 ratio. Eligible patients will be randomized (1:1:1) into the following cohorts:

- Cohort 1 (High Dose): 2 x 100 mg tablets for 200 mg BOS-589 twice daily (bid) orally;
- Cohort 2 (Low Dose): 2 x 25 mg tablets for 50 mg BOS-589 bid orally;
- Cohort 3 (Placebo): 2 x visually matching Placebo oral tablets bid.

Patients will be assigned to the cohorts using a permuted block randomization stratified by site (44 patients per cohort). The randomization schedule will be generated by an independent unblinded Biostatistician and will be transferred to the IWRS team for loading into the system. PPD blinded biostatistics and blinded programming team will remain blinded. The randomization file will be held by the independent unblinded Biostatistician until the end of the trial and when the database has been locked.

The sponsor, site staff, and patients will be blinded to the treatment assignment. BOS-589 and Placebo will be similar in appearance, and provided in white, opaque, high-density polyethylene bottles, each with a child-resistant closure. Each bottle will be labeled as per country requirement.

Only in a medical emergency will a patient's treatment assignment be unblinded, and this process will be performed and documented in the IWRS. Every effort should be made to contact the Medical Monitor to discuss unblinding prior to breaking the blind.

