4.1.2 Number of Patients

Approximately 300 patients will be screened to randomize approximately 132 patients with IBS-D (44 patients per cohort).

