4.1.4 Number of Sites

Up to 66 sites in the United States may participate in this study.

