4. DATA ANALYSIS CONSIDERATIONS

Unless noted otherwise, the following statistical considerations will be applied:

- All analyses will be conducted based on Statistical Analysis System (SAS[®]) software version 9.4 or higher.
- Data for all sites/centers will be pooled for analysis.
- All data in the database except birth date will be presented in by-patient data listings.
- Listings will be sorted by cohort, patient identification number (concatenated site and patient number), and assessment date (and time, if available). If assessment date is missing, chronological visit will be used for sorting.
- Continuous data will be summarized by cohort (or last assigned dose level, as applicable) based on n, mean, median, standard deviation (SD), 25th percentile/first quartile (Q1), 75th percentile/third quartile (Q3), minimum value, and maximum value.
- Categorical data will be summarized by cohort using n and percentage based on the number of non-missing values.
 - The number of missing values will be presented as a separate category with no percentage, but only if one or more patients are missing data.
 - Counts of zero will be presented without percentages.
- Statistics will be presented in the summary tables based on the following:
 - Mean, Median, Q1, and Q3: one additional decimal place to that reported for Minimum and Maximum
 - SD: two additional decimal places than the Minimum and Maximum

- Percentages: reported to one decimal place
- P-values will be reported to four decimal places. If the value is below 0.0001 it will be noted as < 0.0001; if the value above 0.9999 it will be noted as > 0.9999.
- The number and percentage will be presented in the form of XX (XX%). Percentage values of less than 1% will be presented as XX (<1%).
- Statistical inference will be based on a 5% significance level (i.e., 95% confidence intervals [CIs] will be produced). CIs will be produced only in cases with sufficient sample size (i.e., n => 5).
- Change from baseline = value (post-baseline visit) – value (baseline or last visit prior to treatment).
- All data up to the time of study completion/withdrawal from the study will be included in the analysis, regardless of duration of treatment.
- Numbering for data displays will be based on the International Council for Harmonization E3.
- The protocol uses the terms cohort, treatment group, and treatment arm interchangeably. For consistency in this document, the term cohort will be used.

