4.1. Stratification and Covariates

There are no formal plans for analysis stratification or use of covariates.

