7.1. Primary Efficacy Endpoint and Analyses

7.1.1. Worst Abdominal Pain

The primary efficacy endpoint will be defined as a change in the 24-hour WAP score at the Day 29 visit compared to baseline (averaged over the week prior to the visit). The 24-hour WAP score will be a patient-reported score of their WAP in the past 24 hours on a 0 to 10 scale, where 0 corresponds to no pain and 10 corresponds to worst imaginable pain. Patients will be asked to rate their WAP in the past 24 hours every day for the entire Run-in period and the 4-week double-blind treatment period.

This is a proof-of-principle study in which a hierarchical hypothesis test will be employed for the primary efficacy endpoint. The mean change in 24-hour WAP at the Day 29 visit from baseline (averaged over the week prior to the visit) will be measured as a continuous variable and compared between cohorts in the following testing order using a t-test of equal variances and a two-tailed alpha of 0.05:

Hypothesis 1:

Active Treatment (Cohort 1 + Cohort 2) versus Placebo (Cohort 3);

$$H_0: \mu_1 = \mu_2$$

$$H_1: \mu_1 \neq \mu_2$$

The null hypothesis will be that there is no difference in the mean change in 24-hour WAP score at the Day 29 visit from Baseline (averaged over the week prior to the visit) between active treatment and Placebo. The alternative hypothesis will be that there is a difference in the mean change in 24-hour WAP score at the Day 29 visit from Baseline (averaged over the week prior to the visit) between active treatment and Placebo. The test statistic is:

$$t = \frac{\bar{x}_1 - \bar{x}_2}{\sqrt{s^2(\frac{1}{n_1} + \frac{1}{n_2})}}$$

\bar{x}_1 and \bar{x}_2 are the sample means of change at the Day 29 visit from Baseline in 24-hour WAP score (averaged over the week prior to the visit), s^2 is the pooled sample variance assuming equal variance, n_1 and n_2 are the sample sizes, and the degree of freedom is $n_1 + n_2 - 2$.

If statistically significant at $P < 0.05$, then proceed to Hypothesis 2.

Hypothesis 2:

Cohort 1 (High Dose) versus Cohort 3 (Placebo);

Sponsor: Boston Pharmaceuticals, Inc.
Protocol Number: BOS-589-201
Version and Date: Version 1.2 12NOV2020

If statistically significant at $P < 0.05$, then proceed to Hypothesis 3.

Hypothesis 3:

Cohort 2 (Low Dose) versus Cohort 3 (Placebo);

If statistically significant at $P < 0.05$ then, proceed to Hypothesis 4.

Hypothesis 4:

Cohort 1 (High Dose) versus Cohort 2 (Low Dose).

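### The primary t-test ignores the site stratification used in randomization; if sites differ in mean change, it is conservative and gives up a little power

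*SAP*

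**What the plan says.** SAP 3.3 sets the allocation: "Patients will be assigned to the cohorts using a permuted block randomization stratified by site (44 patients per cohort". Protocol 6.3 and SAP 5.1 describe the same scheme. Protocol 4.1.4 allows many sites: "Up to 66 sites in the United States may participate in this study". Protocol 4.1.2 gives the size: "Approximately 300 patients will be screened to randomize approximately 132 patients with IBS-D (44 patients per cohort".

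The analysis does not carry the stratification forward. SAP 4 says "Data for all sites/centers will be pooled for analysis", and SAP 4.1 says "There are no formal plans for analysis stratification or use of covariates". Under SAP 7.1.1 the mean changes are "compared between cohorts in the following testing order using a t-test of equal variances and a two-tailed alpha of 0.05". In that test statistic, s² "is the pooled sample variance assuming equal variance", with no site component. The first and powered comparison is "Active Treatment (Cohort 1 + Cohort 2) versus Placebo (Cohort 3", that is, 2:1.

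Neither document states the block size, the expected enrolment per site, a rule for small sites, the between-site variance, or a site-adjusted sensitivity analysis.

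**The concern.** Blocking within site makes the cohorts more alike in their mix of sites than simple randomization would. Whatever site-to-site variation in mean change exists is therefore partly cancelled from the treatment difference. An unstratified t-test does not know this. Its pooled variance still contains the whole between-site component, so the reported standard error exceeds the true one.

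Some site variation is plausible on the sponsor's own account: Protocol 4.2 justifies multiple sites partly by regional differences in diet, exercise and ethnicity. What is at stake is power. The margin is thin: the planned 120 patients give slightly under 80% for Hypothesis 1, and the single-dose comparisons further down the hierarchy have about 70% at 44 v 44 with the same inputs.

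**Working it through.** **Inputs from the documents.** Difference 1.6, SD 3, two-sided alpha 0.05, N = 120 raised to 132 (SAP 3.4); 1:1:1 allocation, so Hypothesis 1 is 80 v 40 at N = 120 and 88 v 44 at N = 132. **Assumed, because the documents do not give them:** ICC 0 to 0.20, block size, and patients per site.

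**The plan's own figure.** SE = SD × √(1/n₁ + 1/n₂); power ≈ Φ(1.6/SE − 1.96).
- 80 v 40: SE = 3 × √(1/80 + 1/40) = 0.581; power 78.6% (78.0% by noncentral t). The stated approximate 80% is reproduced.
- 88 v 44: SE = 0.554; power 82.3% (81.8% by noncentral t).

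**True SE under site-stratified blocks.** Let ρ be the ICC. The t-test reports about 0.554 whatever ρ is.
- *Blocks fill at every site* (for example 44 sites of 3, blocks of 3). Site effects cancel completely: true SE = 0.554 × √(1 − ρ).
- *66 sites of 2, blocks of 3.* The two patients at a site are always in different cohorts. On average 44 sites hold one active and one placebo patient, and 22 hold two active. The site contribution to the variance is ρσ² × [44 × (1/88 − 1/44)² + 22 × (2/88)²] = ρσ² × 132/7744 = 0.0170ρσ². Without stratification it would be (1/88 + 1/44)ρσ² = 0.0341ρσ². Half is removed: true SE = 0.554 × √(1 − ρ/2).

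The t-test's size is 2Φ(−1.96 × 0.554/true SE) and its power is Φ((1.6 − 1.96 × 0.554)/true SE). The random-intercept column is generalized least squares with known ICC.

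| Layout | ICC | True SE | Reported/true | Size of t-test | Power, t-test | Power, random intercept |
|---|---|---|---|---|---|---|
| Any | 0 | 0.554 | 1.00 | 5.0% | 82.3% | 82.3% |
| 66 × 2 | 0.05 | 0.547 | 1.013 | 4.7% | 82.7% | 83.4% |
| 66 × 2 | 0.10 | 0.540 | 1.026 | 4.4% | 83.0% | 84.5% |
| 66 × 2 | 0.20 | 0.525 | 1.054 | 3.9% | 83.6% | 87.1% |
| Blocks fill | 0.05 | 0.540 | 1.026 | 4.4% | 83.0% | 84.2% |
| Blocks fill | 0.10 | 0.525 | 1.054 | 3.9% | 83.6% | 86.1% |
| Blocks fill | 0.20 | 0.495 | 1.118 | 2.8% | 85.0% | 89.8% |

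Simulated site-stratified blocks (4000 runs per scenario) agree within simulation error. With 66 equal sites and blocks of 6, stratification balances very little, and the ratio stays at 0.99 to 1.02 up to ICC 0.20.

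**With the site variance estimated rather than known** (REML, 66 sites of 2, blocks of 3, 6000 runs), t-test v random-intercept power was 82.4 v 83.2% at ICC 0.05, 82.1 v 84.3% at 0.10, and 82.5 v 86.0% at 0.20. The site variance was estimated as zero in about 38% of runs at ICC 0.05 and 23% at 0.10. At ICC 0 the model's size was 6.0%, against 5.6% for the t-test in the same runs (Monte Carlo error about 0.3 point).

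**Site as a fixed effect, 66 sites of 2.** Only the 44 mixed sites contribute: SE = 3 × √(2(1 − ρ)/44). At ρ = 0 this is 0.640, power 71%; at 0.05, 73%; at 0.10, 75%; at 0.20, 0.572, power 80%. Every value is below the unadjusted t-test. Blocks of 6 are worse (61 to 70%).

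**The case against.** The strongest reply is that the loss is conditional, small and in the safe direction. The SE is too wide only if sites differ in mean change. The endpoint is a diary-recorded change from baseline in one country, so stable site differences in pain level largely cancel. At the design inputs the t-test at 132 patients stays above 80% at every ICC tried. All of this stands, and it limits how hard the point can be pressed. It does not explain why a factor used to randomize is left out of the analysis without a stated reason.

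Two stronger readings are tempting and are not supported.
- *That the standard error is wrong as a matter of fact.* The documents give no site variance. At ICC 0 the t-test is correct.
- *That 44 per cohort cannot be delivered, because 66 sites share 132 patients.* Sixty-six is a ceiling, 44 is a target alongside an approximate total, and the block size is not stated. With 22 or 44 equal sites and blocks of 3 the split is exactly 44/44/44. With 66 equal sites a cohort's size has an SD of 3.8 (blocks of 3) to 4.9 (blocks of 6), but mean power for Hypothesis 1 is 81.7% or 81.3%, against 81.8% at an exact split: 0.5 point or less. Nothing in the plan depends on exactly 44. Nor is this a reason for study-wide blocks, which would discard the balance within sites.

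**Conclusion.** The mismatch between design and analysis is real; its consequence is modest. If sites differ, the primary t-test is conservative. At assumed ICCs of 0.05 to 0.10 the SE is overstated by about 1 to 5% and about 1 to 3 power points are given up; at ICC 0.20 the loss is about 4 to 5 points. It is nil at ICC 0 and close to nil with 66 equal sites and blocks of 6. These figures rest on the plan's difference of 1.6 and SD of 3 and on assumed ICCs, block sizes and site sizes. There is no inflation of type I error, so a positive result under the planned test would not be undermined by this point. It is an efficiency gain worth taking, not a threat to validity.

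**What to change.** Analyse the primary endpoint, for all four hypotheses in their existing order, in a linear model with cohort as a fixed effect, a random intercept for site, and a small-sample degrees-of-freedom correction such as Kenward–Roger. Do not fit site as a fixed effect. State how the pooled-active comparison is formed as a contrast.

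The t-test and the no-stratification statements appear in several places, so the edit must reach SAP 3.4, 4 (the pooling bullet), 4.1, 4.3 and 7.1.1, and the matching text in the Protocol synopsis, 9.2 and 9.4.1.1. Protocol 9.4 requires a protocol amendment for a major change to the primary analysis, and the change must be made before unblinding. If the sponsor prefers to keep the t-test as primary, prespecify this model as a sensitivity analysis; Protocol 9.4.1.4 already contemplates sensitivity analyses.

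The costs are the amendment, a result that reverts essentially to the unadjusted one when the site variance is estimated as zero, and a size that can run slightly above 5% with estimated variance, which is why the degrees-of-freedom correction is needed. No additional patients or data are required.

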3.4. Sample Size Considerations

This is a phase 2a study in which a hierarchical hypothesis test will be employed for the primary efficacy endpoint. The primary endpoint is defined as a change in the 24-hour WAP score at Day 29 compared to baseline (averaged over the week prior to each respective timepoint). Mean change from baseline will be measured as a continuous variable and compared between cohorts in a hierarchical testing order using a t-test of equal variances and a two-tailed alpha of 0.05.

Sponsor: Boston Pharmaceuticals, Inc.
Protocol Number: BOS-589-201
Version and Date: Version 1.2 12NOV2020

The sample size was based on the first hypothesis test in the hierarchical plan, with approximately 80% power, two-sided alpha of 0.05, and a standard deviation (SD) of 3 points on the numeric rating scale to detect a 1.6 minimum change between cohorts (N = 120 patients). To account for attrition and a potential higher Placebo rate, a total of 132 patients will be randomized to one of 3 cohorts in a 1:1:1 ratio (44 patients per cohort).

3.5. Safety Monitoring Committee

There is no safety monitoring committee reviewing data for this study.

3.6. Interim Analysis

No formal efficacy interim analysis is planned for the purposes of statistically comparing the data prior to the completion of the study.

3.7. Timing of Analyses

Formal hypothesis testing will occur at the end of the study and post database lock. There are no planned Data, Safety, or Adjudication Committees for this study and no planned statistical interim analyses.

4. DATA ANALYSIS CONSIDERATIONS

Unless noted otherwise, the following statistical considerations will be applied:

- All analyses will be conducted based on Statistical Analysis System (SAS[®]) software version 9.4 or higher.
- Data for all sites/centers will be pooled for analysis.
- All data in the database except birth date will be presented in by-patient data listings.
- Listings will be sorted by cohort, patient identification number (concatenated site and patient number), and assessment date (and time, if available). If assessment date is missing, chronological visit will be used for sorting.
- Continuous data will be summarized by cohort (or last assigned dose level, as applicable) based on n, mean, median, standard deviation (SD), 25th percentile/first quartile (Q1), 75th percentile/third quartile (Q3), minimum value, and maximum value.
- Categorical data will be summarized by cohort using n and percentage based on the number of non-missing values.
 - The number of missing values will be presented as a separate category with no percentage, but only if one or more patients are missing data.
 - Counts of zero will be presented without percentages.
- Statistics will be presented in the summary tables based on the following:
 - Mean, Median, Q1, and Q3: one additional decimal place to that reported for Minimum and Maximum
 - SD: two additional decimal places than the Minimum and Maximum

- Percentages: reported to one decimal place
- P-values will be reported to four decimal places. If the value is below 0.0001 it will be noted as < 0.0001; if the value above 0.9999 it will be noted as > 0.9999.
- The number and percentage will be presented in the form of XX (XX%). Percentage values of less than 1% will be presented as XX (<1%).
- Statistical inference will be based on a 5% significance level (i.e., 95% confidence intervals [CIs] will be produced). CIs will be produced only in cases with sufficient sample size (i.e., n => 5).
- Change from baseline = value (post-baseline visit) – value (baseline or last visit prior to treatment).
- All data up to the time of study completion/withdrawal from the study will be included in the analysis, regardless of duration of treatment.
- Numbering for data displays will be based on the International Council for Harmonization E3.
- The protocol uses the terms cohort, treatment group, and treatment arm interchangeably. For consistency in this document, the term cohort will be used.

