7 DISCONTINUATION / WITHDRAWAL

7.1 Discontinuation of Investigational Product

A patient may discontinue from study treatment at any time at his or her own request or may be withdrawn at any time at the discretion of the Investigator for safety, behavioral, or administrative reasons. Discontinuation from the investigational product does not mean discontinuation from the study, and remaining study procedures should be completed as indicated by the study protocol. If a clinically significant finding is identified (including, but not limited to, changes from baseline) after enrollment, the Investigator or qualified designee will determine if any change in patient management is needed. Any new clinically relevant finding will be reported as an AE.

Upon investigational product discontinuation, patients should complete all procedures collected in the Day 29/End-of-Treatment visit as applicable per the Schedule of Activities ([Section 1.3](#)).

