7. EFFICACY

Efficacy analyses will be conducted using the ITT and PP Analysis Sets.

All available efficacy data will be provided in by-patient data listings on all ITT patients.

The efficacy objectives of the study are to evaluate the effect of BOS-589, relative to Placebo after 4 weeks of therapy, on pain, defecation, and key IBS-D related signs and symptoms.

During the 4 weeks of the double-blind treatment phase, patients will be required to access their electronic diary every day, preferably at the same time each day, to record IBS-D symptom data and information related to their bowel function and rescue medication use.

For all efficacy endpoints, the Day 29 visit change from baseline is the main timepoint of interest. However, unless stated otherwise, data will be presented for each planned visit (Baseline/Day 1, Day 8, Day 15, Day 22, Day 29, and Day 43).

For efficacy endpoints collected daily, the baseline score will be the average of non-missing scores reported for the last 7 days prior to the date where eligibility and run-in criteria pertaining to IBS-D symptom and bowel function have been met. The Day 29 visit score will be the average of non-missing scores reported during the 7 days prior to the Day 29 visit. The Day 8 visit, Day 15 visit, Day 22 visit, and Day 43 visit scores are calculated in a similar manner. If there are missing daily scores on any day, the visit score will be averaged from all the non-missing values during the 7 days prior to the visit. No imputation of the missing values will be made. For the Day 29 calculation only, a window of ± 14 days relative to actual calculated day 29 from dosing will be applied such that any Day 29 visit occurring outside that window will be excluded.

Sponsor: Boston Pharmaceuticals, Inc.
Protocol Number: BOS-589-201
Version and Date: Version 1.2 12NOV2020

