7.3. Exploratory Efficacy Endpoints and Analyses

7.3.1. Weekly Responder

Weekly responders will be summarized as an exploratory efficacy endpoint.

A patient is categorized as a weekly responder if the patient is a weekly responder in both pain intensity and stool consistency (page 8 of [FDA guidance document on IBS](#)).

- An Abdominal Pain Intensity Weekly Responder is defined as a patient who experiences a decrease in the weekly average of the WAP in the past 24 hours score of at least 30 percent compared with weekly average at baseline, i.e., $(\text{weekly average of baseline} - \text{weekly average of a post-baseline visit}) / \text{weekly average of baseline} \geq 0.3$
- A Stool Consistency Weekly Responder is defined as a patient who experiences a 50 percent or greater reduction in the number of days per week with at least one stool that has a consistency of Type 6 or 7 compared with weekly average at baseline, i.e., $(\text{weekly average of the number of Type 6 or 7 BSFS stool of baseline} - \text{weekly average of the number of Type 6 or 7 BSFS stool of a post-baseline visit}) / \text{weekly average of the number of Type 6 or 7 BSFS stool of baseline} \geq 0.5$

The number and percentage of patients who are abdominal pain intensity weekly responders, stool consistency weekly responder, and composite weekly responders in both will be summarized by cohort at each scheduled visit. A chi-square test will be used, as a reference, to test whether there is a difference by between each active dose level and Placebo, both active dose levels and Placebo, and between the two active dose levels. Fisher's exact test will be used if the expected values in any of the cells of the contingency table are below 5.

To evaluate the treatment effects in the subset of patients with fecal calprotectin under 50mcg/g at screening, this analysis of weekly responders will be repeated as a sensitivity analysis on this subgroup.

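### Weekly responder percentages leave out ITT patients without data at a visit, and the stool component's words and formula differ with no rule for unrecorded diary days

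*SAP*

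**What the plan says.** Three parts of the SAP bear on the denominator.

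- SAP 4 gives the default: "Categorical data will be summarized by cohort using n and percentage based on the number of non-missing values". The sub-bullet beneath it adds: "The number of missing values will be presented as a separate category with no percentage".
- SAP 7.3.1 reports "The number and percentage of patients who are abdominal pain intensity weekly responders, stool consistency weekly responder, and composite weekly responders in both" by cohort at each visit. It names no denominator and does not say how a patient without data is classified.
- SAP 7 states: "No imputation of the missing values will be made". For Day 29 it applies a window of 14 days either side of the calculated day, and "any Day 29 visit occurring outside that window will be excluded".

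The ITT set in SAP 6.1 is all randomised patients.

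On diary days within a week, SAP 7 has a rule for endpoints collected daily: "If there are missing daily scores on any day, the visit score will be averaged from all the non-missing values". SAP 7.3.1 words the stool responder as a "50 percent or greater reduction in the number of days per week with at least one stool" of Type 6 or 7. The formula that follows works instead with a weekly average of the number of Type 6 or 7 stools. No minimum number of post-baseline diary days is given. Entry, by contrast, requires diary completion on at least 6 of the 7 days before randomisation (Protocol 5.1 and 8.2).

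**The concern.** A responder percentage in an ITT table is normally read as a share of the patients randomised. Under the SAP 4 default it is a share of those who still had data. The two differ by a factor that grows with dropout. If dropout differs between arms, the table can show a difference that is not there or mask one that is.

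The stool component adds a second uncertainty. A count of days can only fall when days go unrecorded, whereas a proportion of recorded days need not. Baseline is nearly complete by design and later weeks have no floor, so a count would tend to favour patients who keep a poor diary. The composite responder is modelled on the FDA guidance definition, and the trial is meant to inform dose selection (SAP 3.1). The numbers may therefore be used even though the endpoint is exploratory.

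**Working it through.** **Source of the dropout figure.** The documents state no figure for the responder endpoint. The only attrition allowance is in the sample size section (SAP 3.4): 120 evaluable, 132 randomised, 44 per cohort. With 40 placebo against 80 active, a difference of 1.6, SD 3 and two-sided alpha 0.05, the normal approximation gives 78.6% power, in line with the stated approximate 80%. The allowance is (132 − 120)/132 = 9.1%, or 4 of 44 per cohort. The SAP says that this margin also covers a higher placebo rate, so 9.1% reads all of it as attrition.

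**Denominator.** If d of 44 patients lack data and x respond, the default reports x/(44 − d) and the all-randomised rate is x/44. The ratio is 44/(44 − d). The 40% response and the losses above 4 are assumptions.

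| Missing per cohort | Reported rate | Same responders over 44 | Ratio |
|---|---|---|---|
| 4 (plan's allowance) | 16/40 = 40.0% | 16/44 = 36.4% | 1.10 |
| 9 (assumed) | 14/35 = 40.0% | 14/44 = 31.8% | 1.26 |

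With unequal loss, take 14 responders of 44 in each of two arms, with 9 missing in one and 4 in the other (assumed). The table then reads 14/35 = 40.0% against 14/40 = 35.0%. That 5-point gap comes only from missing data.

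**Stool component, two readings.** Take a patient whose true rate of loose days does not change. Assume that 80% of days are loose, days are independent and all 7 baseline days are recorded. Let B be the number of loose baseline days, binomial(7, 0.8), conditional on B ≥ 2 because entry requires at least 2 such days. Let K be the number of loose days among m recorded post-baseline days, binomial(m, 0.8).

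- Count reading: responder if K ≤ B/2.
- Proportion reading: responder if K/m ≤ (B/7)/2.

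| Recorded post-baseline days (m) | Count | Proportion |
|---|---|---|
| 7 | 2.1% | 2.1% |
| 5 | 17.4% | 3.6% |
| 4 | 41.2% | 5.9% |
| 3 | 77.1% | 9.0% |

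As a single case, 6 loose days at baseline followed by 3 recorded days, all loose, gives (6 − 3)/6 = 0.5. That meets the threshold on the count. On the proportion scale, 3/3 is no improvement.

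**Sensitivity.** With 60% to 90% of days loose and 3 recorded days, the count reading gives 70% to 89% and the proportion reading 3% to 19%. With 6 baseline days recorded instead of 7 (still 80% loose), the count figures at 5, 4 and 3 recorded days fall to 11%, 27% and 59%. With one missed post-baseline day and 7 at baseline, the count reading gives about 6%.

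**The case against.** A reader might infer that the SAP treats a missing diary day as a day without loose stools. The documents do not support that. The SAP 4 sentence concerns patients in a denominator, not days in a week. The only stated rule for daily data averages the recorded values, and the formula in 7.3.1 also speaks of an average. Someone who applied that rule to a daily Type 6 or 7 indicator would arrive at the proportion proposed here. The count-reading figures therefore measure an ambiguity, not a stated rule.

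The ambiguity itself stands. The formula averages a number of stools, but the diary described in SAP 7.2.1 and 7.2.2 yields two daily form scores and a total stool count, with no count of Type 6 or 7 stools. A programmer cannot follow the formula literally, and the worded alternative is a count of days.

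Four further limits are fair:

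- Only the stool component, and the composite through it, is exposed. Pain is a weekly average, and a composite response also needs a 30% pain reduction.
- The number missing is displayed, so a reader can rebuild the all-randomised rate. Equal dropout with equal response among those observed scales the arms alike.
- Not every early stopper leaves the table. Protocol 7.1 says: "Upon investigational product discontinuation, patients should complete all procedures collected in the Day 29/End-of-Treatment visit". A visit from Day 15 to Day 43 falls inside the window; one before Day 15 does not.
- Counting missing as non-response is a convention, not the truth. It is the usual reading of an ITT responder rate, but it too is an assumption.

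**Conclusion.** The denominator point holds on the text. By default, responder percentages exclude ITT patients without data at the visit, and the reported rate exceeds the rate that counts them as non-responders over all randomised. The excess is a factor of 1.10 at the plan's own allowance and 1.26 if 9 of 44 are missing. Any distortion between arms depends on unequal missingness, for which the documents give no figure.

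The diary-day point holds only as a gap in the definition. Words and formula differ, no rule says how an unrecorded day enters, and no minimum number of post-baseline days is set. The false-response figures of 2%, 17%, 41% and 77% apply only if the worded count is programmed, only to the stool component, and only under the assumed 80% of days loose with 7 baseline days. Nothing in the documents suggests that weeks with 3 or 4 entries will be common.

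The endpoint is exploratory and its chi-square test is for reference only. The primary hierarchy and the sample size do not depend on it. The change is worth making before unblinding because it is cheap.

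**What to change.** In SAP 7.3.1:

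1. Define the stool responder as at least a 50% reduction from baseline in the proportion of recorded diary days with a worst BSFS of 6 or 7, and rewrite the formula to match.
2. State what makes a week evaluable, that is, the minimum number of recorded days. The proportion rule alone still gives 9% false response with 3 days under the assumptions above.
3. Count ITT patients with no evaluable week at a visit as non-responders for all three responder summaries, with all randomised patients in the cohort as denominator. State this as an exception to the SAP 4 default.
4. Keep the observed-case table as supportive.

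The cost is SAP wording, one extra table and somewhat lower reported response rates.
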